# 2. Subject Population

[1] Medical professionals track: All participants (over 17) who have matriculated to the Tulane University Health Sciences Center as students or residents in addition to physicians participating in the curriculum as continuing medical education (CME) credits for a target sample of 10,000 respondents. Subjects will be offered the survey from medical school through residency and into medical practice. Up to 1,000 marketing students will be offered a self-regulation survey.

[2] Community track: Adults 17 years and older and children 7-17 in the Greater New Orleans area for a target sample of 6,000 subjects (3,000 taking the classes and the rest not). Subjects will be followed for three years after their class participation or lack thereof based upon standards for such studies.

[3] Employee track: Employees and their family members 7 years and older affiliated with Laitram, LLC for a target sample of 3,000 subjects (1,500 taking the classes and the rest not). Subjects will be followed for three years after their class participation or lack thereof based upon standards for such studies.

[4] RCT track: Adults 17 years and older with diagnosed diabetes, hypertension, hyperlipidemia, cardiovascular disease, or past history of cerebrovascular disease or their pre-diagnosis conditions (i.e. pre-diabetes as the condition at risk for developing diabetes) for a target sample of 500 subjects. Subjects will be followed for three years after their class participation or lack thereof based upon standards for such studies.

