CHOP is a prospective observational cohort study with four tracks ([1] medical professionals, [2] community, [3] employee, and [4] randomized controlled trial [RCT]) to allow results to be compared among the subjects in the four tracks. [1] Current and future medical professionals will be trained in classes within their track in how to educate patients about nutrition, and their results for their DACs will be compared to those who receive traditional clinical education. [2] Adults, adolescents, and children 7 years and older will be offered classes in their community track to allow comparison of their DACs and health metrics with those who do not take the classes. [3] Employees and their families who take the GCCM classes as employee wellness programing will have their DAC and health metrics compared to employees who do not take the classes. And finally, [4] subjects with such chronic health conditions as diabetes will be randomized with equal 50% chance to either taking the GCCM classes or receiving medical nutrition therapy (MNT) with a registered dietician (RD).

DAC surveys will take place for the first track at the beginning and end of each academic year. Surveys will take place for the last three tracks at the first and last class for the treatment (GCCM) class group, and the beginning of the study and 2-3 months later for the control groups (those who do not take the classes). The same adult and children surveys will be used across tracks [2]-[4] for adults 18 years and older and children 7-17 respectively. Medical professionals in [1] will have the same survey.

CHOP unites such analyses as diffusion of innovation (DOI), social network, and simulation-based medical education with deliberate practice (SBME-DP) along with rigorous statistical methods to answer these questions and hopefully benefit society. Results will be strengthened by using self regulation survey with Tulane marketing students to better design the DAC survey based on understanding what DACs predict

Version Date: 09/26/15 Version Number: 1 Page 2 of 9 certain nutrition behavior, in addition to comparison to the de-identified National Health and Nutrition Examination Survey (NHANES) for national trends in diet and similar health metrics and behaviors.

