# 3. Procedure

[1] Medical professionals track: An internet link will be distributed to subjects through the list-serves for each class at the beginning and end of each academic year after they have had the opportunity to participate or not in the voluntary GCCM classes. Residents and practicing physicians who identify themselves through the GCCM website will be subsequently offered the survey. Marketing students will be offered an online survey about self-regulation and nutrition through their marketing class to improve the medical professionals survey.

[2] Community, [3] Employee, and [4] RCT tracks: Subjects in the treatment group will receive up to 20 evidence-based classes (50 hours) of cooking and nutrition education that cover the Mediterranean diet, food shopping, cooking, and storage. Subjects in the control groups for [2] and [3] will not receive the classes, and control subjects in [4] will receive MNT. Control subjects in [2] will additionally have the opportunity to receive either healthy food vouchers for 2 months or have nutrition education for their children before they enroll in the classes in order to compare if increased healthy food access and education compared to GCCM classes best prepares them to benefit from nutrition education. DAC surveys will be used at the beginning and end of the classes for the treatment group, and beginning of the study and 2-3 months later for the control group. Health metrics will be assessed from health records for subjects retrospectively 3 years before and 3 years after their treatment or control exposure, once subjects provide release to the study team of their records with appropriate safeguards to protect

Version Date: 09/26/15 Version Number: 1 Page 3 of 9 the safety of their data. Recruitment for [2] will be through GCCM's website, [3] will be through Laitram that promotes the classes to their employees, and [4] through Tulane University Hospital and Clinic (including the Internal Medicine Practice, Uptown Square clinic, Endocrinology clinic, and Metairie Multispecialty clinic) by study staff. Health metrics will be obtained for [2,4] from Tulane University Hospital and Clinic if subjects' information is stored there, from Marathon Health the third party provider of health care for [3], and from non-Tulane health care institutions for [2,4]. Marathon and non-Tulane facility health information release forms will be provided to subjects as needed at the time of informed consent.

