#### 10. Consent process and documentation

[1] Medical professionals track: A waiver of documentation of consent has been attached to this package for both medical professionals and trainees and marketing students, due to the information necessary for informed consent being provided in the recruitment email and the significant logistical challenges of documenting consent individually for such a large number of respondents remotely accessing the survey through the confidential online survey link. Email addresses are collected to verify the accuracy of the self-generated dummy IDs for subjects who respond to repeat surveys, and then the emails are deleted from the dataset used for longitudinal analysis.

[2] Community, [3] Employee, and [4] RCT tracks: A full description of the research will be discussed with subjects regarding both study groups. Discussion about the risks and benefits will be undertaken with prospective participants. This will mirror the written information in the consent form. After full information is discussed and questions are answered the participants the consent form will be reviewed and subjects will be asked to sign the form if they are interested in being involved (adults) or assent (children). Telephone numbers are collected based on GCCM experience over the past four years that class participants find reminders about classes helpful.

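### Tracks 2–4 neither exclude nor identify people who took GCCM classes before enrolment, so no-class groups and the 3-year look-back can contain earlier exposure (best supported for track 2)

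*Combined protocol and SAP*

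**What the plan says.** Section 2 (Subject Population) gives the whole entry rule for each track:

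- Track 2: "Adults 17 years and older and children 7-17 in the Greater New Orleans area for a target sample of 6,000 subjects", half taking the classes and half not.
- Track 3: "Employees and their family members 7 years and older affiliated with Laitram, LLC for a target sample of 3,000 subjects", again split in half.
- Track 4: "Adults 17 years and older with diagnosed diabetes, hypertension, hyperlipidemia, cardiovascular disease, or past history of cerebrovascular disease or their pre-diagnosis conditions", for 500 subjects. Section 1 randomises them with equal chance to the classes or to medical nutrition therapy (MNT).

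Section 3 (Procedure) sets the window for health outcomes: "Health metrics will be assessed from health records for subjects retrospectively 3 years before and 3 years after their treatment or control exposure". It also names the recruitment channel for the community track: "Recruitment for [2] will be through GCCM's website".

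Section 10 (Consent process and documentation), in its paragraph on tracks 2–4, says: "Telephone numbers are collected based on GCCM experience over the past four years that class participants find reminders about classes helpful".

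**The concern.** The intervention already existed when the protocol was written, and the provider had several years of participants. The entry rules do not ask whether a candidate was one of them.

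This matters in two ways. A past attender enrolled as a control may already carry some of the effect that the study wants to measure. A past attender in either group may also have post-class time inside the window that serves as the baseline. Track 2 is the most exposed, because past participants are likely to return to the provider's own website.

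The entry rules of the tracks also overlap, and nothing limits a person to one track. Someone who is a control in one track could therefore receive the classes through another.

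**Working it through.** **1. Is there a rule anywhere?** Section 2 uses age with area, affiliation or diagnosis, and nothing else. Section 3 says that controls in tracks 2 and 3 do not get the classes, which governs conduct during the study and is silent on earlier attendance. No washout, attendance record or one-track rule appears. The nearest analytic control is the SAP's covariate for prior nutrition education. It sits beside school year, intended specialty and medical school, so it belongs to the medical-trainee model. It does not single out GCCM classes, and no covariate can restore a baseline record that is already post-class.

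**2. Timeline.** The page footer reads "Version Date: 09/26/15 Version Number: 1".
- September 2015 − 4 years (section 10) = about September 2011, the latest start of GCCM classes.
- September 2015 − 3 years (section 3) = about September 2012, the start of the look-back for a subject exposed at the version date.

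For anyone exposed on or after the version date, the whole look-back lies in a period when GCCM was already running classes of some kind.

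**3. Size.** The documents give no count of past participants, so p and k below are assumptions. Let d be the true effect, p the share of controls who attended earlier, and k the fraction of the effect they keep (0 to 1).

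Contrast = d − k·p·d = (1 − k·p)·d

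With full carry-over, k = 1, the upper case for a given p:

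| p | contrast kept | loss | track 2 controls this implies (of 6,000 − 3,000 = 3,000) |
|---|---|---|---|
| 5% | 0.95 d | 5% | 150 |
| 10% | 0.90 d | 10% | 300 |
| 20% | 0.80 d | 20% | 600 |

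With k below 1 the loss lies between 0 and p.

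On the odds-ratio scale, take a true OR of 1.50 and an assumed control rate of 20%. The treated rate is 0.20 × 1.5 / (0.80 + 0.20 × 1.5) = 27.3%. With p = 20%, the control rate becomes 20% + 0.20 × 7.27% = 21.5%, and the OR falls to about 1.37.

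The SAP's only calculated figure, 263 cases for an OR of 1.50, gives no base rate or allocation and cannot be reproduced from what is stated. Nothing here depends on it.

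**4. Before/after change.** If a share q of the class group attended before the look-back began, kept the full effect and gained nothing from repeating, the mean change is (1 − q)·d. If they attended part-way through the look-back, the baseline is a mixture of pre-class and post-class time.

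**5. Direction.** In track 4, allocation is random, so earlier attendance is balanced in expectation. Under the same assumptions, attenders add no contrast in either arm, and the result is dilution only, to (1 − p)·d against MNT. In tracks 2 and 3 people choose whether to take the classes. If returners concentrate in the class group, and are keener or build on what they learned before, the contrast could be inflated.

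**6. Overlap.** An adult Laitram employee with diabetes who lives in Greater New Orleans meets the rules of tracks 2, 3 and 4 together. As a track 3 control or a track 4 MNT subject, that person may still join the classes under track 2.

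**The case against.** The strongest case on the other side is that much of this is inferred from silence.

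- **Who attended, and what.** Section 10 does not say who the earlier participants were, how many there were, or whether they took the programme of up to 20 classes described in section 3. A reader might infer that the same intervention had been on offer to all three populations. The documents do not support that. A 2014 title in the reference list concerns community cooking classes, and a 2015 title concerns a teaching-kitchen trial in type 2 diabetes. These are suggestive only. Nothing shows earlier attendance by Laitram staff or by patients of the track 4 clinics. This stands, and it is why the point centres on track 2.
- **Coding.** A reader might infer that sites are told to count past attenders as unexposed. No coding rule is written. Section 1 describes controls as people who do not take the classes, which is compatible with leaving past attenders out. The fault is an omission, not an instruction to misclassify.
- **Certain bias to nil.** This cannot be claimed for the self-selected tracks, as step 5 shows.
- **Double counting between tracks.** Section 1 speaks of comparing subjects among the four tracks, but every comparison it then describes is within a track, and the SAP specifies no between-track test. The tracks also recruit through separate channels, and staff hold a key that identifies participants. What remains is the crossover route in step 6.
- **Small p, small problem.** Nothing suggests as many as 600 past attenders among track 2 controls. If few people would be excluded, the bias is small as well. That is fair, but the plan collects nothing that would show which case applies.
- **Unseen content.** The surveys are given as links only and might ask about earlier classes. Even so, neither section 2 nor the SAP uses such an answer.

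**Conclusion.** The gap is real but modest. By its stated criteria the study can enrol people who have already taken GCCM classes, place them in a no-class group, and count post-class time as baseline. The documents support this best for track 2, through the four years of earlier participants and the recruitment channel. For tracks 3 and 4 it is possible but undocumented.

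The probable consequence is dilution. In track 4 it is dilution only; in tracks 2 and 3 the sign is not assured. The size is unknown. A 5–20% loss of contrast rests entirely on an assumed 5–20% of controls being past attenders with full carry-over. The SAP contains no model or power calculation for tracks 2–4 to which a sample-size penalty could be attached, so none is claimed. The overlap of tracks is a secondary route by which controls could be exposed.

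**What to change.** Add to section 2, for tracks 2–4:

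> Earlier attendance at any GCCM class (with approximate dates) is asked at consent, before allocation in track 4, and checked against class lists where these exist. Past attenders may take the classes but are left out of the primary class-versus-control and before/after comparisons. A sensitivity analysis includes them. Each person enrols in only one of tracks 2–4, checked against the staff code key.

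Because attendance is recorded before allocation, leaving past attenders out of the track 4 comparison does not disturb the randomisation. The one-track rule stops at tracks 2–4 because track 1 has no documented consent and deletes emails from its longitudinal dataset.

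The cost is one question, a list check and a loss of analysable subjects. That loss should be small, but it depends on the same unknown number as the dilution. Whether usable class lists exist is an assumption; self-report alone would still be an improvement.

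This does not deal with track 2 controls who, under section 3, receive vouchers or education for their children and then go on to the classes, possibly within the 3-year follow-up. The analysis needs a separate rule for them.

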# 3. Procedure

[1] Medical professionals track: An internet link will be distributed to subjects through the list-serves for each class at the beginning and end of each academic year after they have had the opportunity to participate or not in the voluntary GCCM classes. Residents and practicing physicians who identify themselves through the GCCM website will be subsequently offered the survey. Marketing students will be offered an online survey about self-regulation and nutrition through their marketing class to improve the medical professionals survey.

[2] Community, [3] Employee, and [4] RCT tracks: Subjects in the treatment group will receive up to 20 evidence-based classes (50 hours) of cooking and nutrition education that cover the Mediterranean diet, food shopping, cooking, and storage. Subjects in the control groups for [2] and [3] will not receive the classes, and control subjects in [4] will receive MNT. Control subjects in [2] will additionally have the opportunity to receive either healthy food vouchers for 2 months or have nutrition education for their children before they enroll in the classes in order to compare if increased healthy food access and education compared to GCCM classes best prepares them to benefit from nutrition education. DAC surveys will be used at the beginning and end of the classes for the treatment group, and beginning of the study and 2-3 months later for the control group. Health metrics will be assessed from health records for subjects retrospectively 3 years before and 3 years after their treatment or control exposure, once subjects provide release to the study team of their records with appropriate safeguards to protect

Version Date: 09/26/15 Version Number: 1 Page 3 of 9 the safety of their data. Recruitment for [2] will be through GCCM's website, [3] will be through Laitram that promotes the classes to their employees, and [4] through Tulane University Hospital and Clinic (including the Internal Medicine Practice, Uptown Square clinic, Endocrinology clinic, and Metairie Multispecialty clinic) by study staff. Health metrics will be obtained for [2,4] from Tulane University Hospital and Clinic if subjects' information is stored there, from Marathon Health the third party provider of health care for [3], and from non-Tulane health care institutions for [2,4]. Marathon and non-Tulane facility health information release forms will be provided to subjects as needed at the time of informed consent.

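### A track 1 odds ratio that includes residents or CME physicians has no comparator sampled independently of the programme, so it is open to selection bias of unknown size and direction

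*Combined protocol and SAP*

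**What the plan says.** Section 1 of the protocol sets the track 1 contrast: professionals are trained in the GCCM classes and "their results for their DACs will be compared to those who receive traditional clinical education". It also fixes the timing: "DAC surveys will take place for the first track at the beginning and end of each academic year".

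Section 2 defines who is eligible. Students and residents enter by matriculation, whatever their class uptake: "All participants (over 17) who have matriculated to the Tulane University Health Sciences Center as students or residents". Other physicians enter as "physicians participating in the curriculum as continuing medical education (CME) credits for a target sample of 10,000 respondents". Follow-up is meant to continue: "Subjects will be offered the survey from medical school through residency and into medical practice".

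Section 3 defines how people are reached, and here the groups part. For school classes, "An internet link will be distributed to subjects through the list-serves for each class at the beginning and end of each academic year". For the rest, "Residents and practicing physicians who identify themselves through the GCCM website will be subsequently offered the survey". It describes no roster, list-serve or other sampling frame for residents or physicians who have not come to the site.

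In the SAP (Machine Learning and Statistical Analysis), the propensity score is the probability of exposure given observed covariates. The regression covariates include prior nutrition education, special diet, year of school and intended specialty. They do not include recruitment channel or career stage after school. The SAP describes no response weighting, selection model or analysis by career stage.

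**The concern.** After medical school, the outcome is measured through the website of the programme being evaluated. Whether a resident or physician is surveyed may then depend both on having taken the classes and on interest in nutrition, which is close to what the DAC survey measures. Two consequences follow.

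- Physicians who enter by the CME route are all exposed. Exposure does not vary among them, so no OR can be estimated within that group, and no covariate or propensity-score adjustment can supply one.
- Unexposed residents may be eligible, but those who reach the survey are non-takers who nevertheless came to the GCCM site. They are not a sample of people who had traditional education. The same holds for former students in practice.

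At stake is the interpretation of resident and physician results, and of any pooled track 1 OR that includes them. Answers never collected from non-takers cannot be recovered at analysis.

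**Working it through.** **1. The plan's own figure.** The SAP's Power Analysis gives 263 cases for 80% power at an OR of 1.50, two-sided 5%. It states neither a baseline rate nor an exposure ratio, so the figure cannot be reproduced uniquely. Comparing two proportions in equal groups needs at least 384 per group. Some unequal splits do give 263 in the smaller group, for example about 3:1 with a 36% baseline. The point here does not depend on this figure; only the OR of 1.50 serves as a yardstick.

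**2. Exposure by route of entry.**

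| Group | Eligible by | Reached by | Unexposed people reachable? |
|---|---|---|---|
| Students | matriculation | class list-serve | yes, irrespective of uptake |
| Residents | matriculation | GCCM website | only if they come to the site |
| Former students in practice | matriculation | GCCM website | only if they come to the site |
| Outside physicians | taking the CME curriculum | GCCM website | none: all exposed |

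**3. Imbalance.** The documents give no rates, so these are assumptions: 40% of residents took classes, and a share s1 of takers and s0 of non-takers self-identify. The exposed share of respondents is 0.4·s1 / (0.4·s1 + 0.6·s0).

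- s1 = 0.20, s0 = 0.02: 0.080 / (0.080 + 0.012) = 87%.
- s1 = 0.10, s0 = 0.05: 0.040 / (0.040 + 0.030) = 57%.

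This shows how thin the comparator could become. It does not show bias: selection on exposure alone leaves the OR unchanged.

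**4. Bias.** Let s(a,y) be the probability of being surveyed for exposure a and outcome y (1 = good DAC). Then

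observed OR = true OR × [s(1,1)/s(1,0)] / [s(0,1)/s(0,0)].

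The distortion is the ratio of the two within-group selection ratios. With a true OR of 1.0 and assumed rates:

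| Exposed, good / not | Unexposed, good / not | Observed OR |
|---|---|---|
| 50% / 50% | 10% / 10% | 1.00 / 1.00 = 1.0 |
| 60% / 40% | 15% / 10% | 1.50 / 1.50 = 1.0 |
| 60% / 40% | 10% / 10% | 1.50 / 1.00 = 1.50 |
| 60% / 30% | 10% / 10% | 2.00 / 1.00 = 2.0 |
| 50% / 50% | 15% / 10% | 1.00 / 1.50 = 0.67 |

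**5. Consequence for the test.** If selection alone produced an OR of 1.5 (50% versus 60%), a two-sided 5% test would be significant in about 37% of studies with 131 per group, 64% with 263 and 80% with 388, against a nominal 5%.

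**6. Whether the SAP corrects it.** The propensity score addresses who took the classes, not who was surveyed. The within-person component needs unexposed and exposed records from the same person. A CME entrant may supply a before-and-after change, but not a contrast with traditional education.

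**The case against.** The strongest objection is scope. The SAP speaks of medical trainees and of repeated observations during medical school, and it adjusts for year of school and intended specialty. The model looks written for students, whose list-serve channel reaches takers and non-takers alike. A reader might infer that the whole track 1 comparison is invalid; the documents do not support that, because the student comparison is untouched. What remains is that residents can be read as trainees and nothing excludes residents or CME physicians from the OR.

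Other strong readings also fail:

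- **All physicians are exposed.** This is true only of those entering through CME. A matriculated student who never took the classes can become an unexposed physician and remain a subject.
- **Former students are lost unless they return to the site.** Section 2 commits to following them, and section 10 mentions a recruitment email. Section 3 does not call the website the sole route. But no document says how former students will be reached or from what list the email is sent, so the follow-up channel is unspecified.
- **No pre-class answer is collected.** In section 3 the survey offer follows self-identification, not the classes, and section 1 plans surveys at both ends of the year with no exception for these groups.
- **Selection produces an OR of 1.50.** That result only returns the selection ratio put in.

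Adjustment for prior nutrition education and special diet may also absorb part of any selection on nutrition interest. This helps only so far as those items capture it.

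**Conclusion.** The concern holds for residents and physicians, and for any pooled track 1 OR that includes them. For CME entrants the gap is complete: there is no unexposed person by that route. For residents and former students in practice, a comparator may exist but is self-selected through the programme's own site. The resulting bias has unknown size and direction. It is nil when selection on DAC is equally strong in both groups, and otherwise equals the ratio of the two within-group selection ratios. All rates used above are assumptions. The track's target of 10,000 is not split by group, so the weight of these groups in a pooled estimate is unknown too. This should be fixed, but it does not undermine the list-serve student comparison.

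**What to change.** (a) State in the SAP that the OR for GCCM versus traditional education is limited to people invited irrespective of class participation. Report CME physicians and website-recruited residents separately and descriptively. The cost is a sentence or two of SAP text and fewer records in the comparative analysis.

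(b) In section 3, invite current residents through programme list-serves, so that takers and non-takers are reached alike. This is a short procedural amendment, and the online survey is already in use.

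(c) Optionally, re-contact former student respondents by email. Section 10 says "Email addresses are collected to verify the accuracy of the self-generated dummy IDs for subjects who respond to repeat surveys" and that the addresses are then removed from the longitudinal dataset. A reader might assume they remain with the code key described in section 4, but no document says so. This step needs an amendment allowing a contact email to be retained for that use, and it must be squared with the waiver of documented consent.

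### Community-track controls are said not to take the classes and then to enrol in them, and no rule classifies their three-year health follow-up after enrolment

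*Combined protocol and SAP*

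**What the plan says.** Protocol section 3 (Procedure) states: "Subjects in the control groups for [2] and [3] will not receive the classes". The next sentence reads: "Control subjects in [2] will additionally have the opportunity to receive either healthy food vouchers for 2 months", or else "have nutrition education for their children before they enroll in the classes". Its stated purpose is to learn which option better prepares people to benefit from nutrition education.

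Section 1 describes the community comparison as a "comparison of their DACs and health metrics with those who do not take the classes" and gives the second survey as "2-3 months later for the control groups (those who do not take the classes". Section 2 splits the community target of 6,000 into 3,000 who take classes and 3,000 who do not, and follows everyone for three years after class participation or its absence.

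On timing, section 3 puts the control surveys at the "beginning of the study and 2-3 months later for the control group". Health metrics come from records "retrospectively 3 years before and 3 years after their treatment or control exposure".

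The SAP describes one analysis. Its clusters are medical institutions, its covariates include school year, intended specialty and medical school, and the exposure in its propensity score (formula 2) carries a subject index but no time index.

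**The concern.** Three statements (section 1, section 2 and the first of the two section 3 sentences) say community controls do not take the classes. One sentence presupposes that they can. A control who enrols then has a control exposure followed by a class exposure, and the health-metric window is anchored to either without saying which applies.

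Two analysts could therefore classify the same person differently in a main community comparison, and both obvious ways of applying the text give a biased contrast. If the person stays a control, class-exposed time counts as control time, the contrast becomes partly early versus delayed classes, and a real effect would usually look smaller. If the person is removed because they later enrolled, the remaining controls have been chosen by what they did after follow-up began. Enrolment is voluntary, so selection could push the result in either direction.

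**Working it through.** The plan gives no figure on this point. The SAP's one sample-size figure (263 cases) comes without a baseline rate or allocation ratio, so it cannot be reproduced, and nothing below uses it.

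**Survey comparison.** Vouchers last 2 months and the second control survey falls at 2-3 months. A control who enrols straight after the vouchers and is surveyed at month 3 is at most 3 - 2 = 1 month into the classes. The overlap is small and avoidable. No duration is given for the children's education option.

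**Health metrics: inputs.**
- From the documents: 3,000 controls (section 2) and 3 years of follow-up (sections 2 and 3), so 3,000 x 3 = 9,000 planned control person-years, before any loss to missing record releases.
- Assumed, because the documents do not say: share f of controls who enrol (10% or 50%); enrolment at month m = 2; a 36-month window opening at study start; an immediate, persistent effect averaged over the window; control label kept after enrolment.

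**Effect retained** = 1 - f x (36 - m)/36.
- f = 0.10, m = 2: 1 - 0.10 x 34/36 = 0.906.
- f = 0.50, m = 2: 1 - 0.50 x 34/36 = 0.528.
- f = 0.50, m = 12: 1 - 0.50 x 24/36 = 0.667.
- If the window opens when the control exposure ends and enrolment is immediate, the formula reduces to 1 - f: 0.90 and 0.50.

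**Control person-years that follow enrolment** = 3,000 x f x (36 - m)/12.
- f = 0.10, m = 2: 850, or 9.4% of 9,000.
- f = 0.50, m = 2: 4,250, or 47.2% of 9,000.

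**The same dilution on the odds-ratio scale.** Take a true OR of 1.50 and a control rate p0 = 0.30. The class-side odds are 1.5 x 0.30/0.70 = 0.643, so p1 = 0.391. With f = 0.50 and m = 2, the diluted control rate is 0.30 + 0.472 x (0.391 - 0.30) = 0.343, with odds 0.522. The observed OR is 0.643/0.522 = 1.23. Over control rates of 0.2-0.5 and enrolment at 2-3 months, it is about 1.44-1.45 with 10% uptake and 1.23-1.25 with 50%. Power at 3,000 per group stays at 0.93 or above with 50% uptake.

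**Precision cost of a remedy** (late-follow-up comparison, equal variances, independent people), as a ratio to the standard error with 3,000 per group:
- Control follow-up ended at enrolment: sqrt[(1/3000 + 1/(3000(1-f)))/(2/3000)] = 1.027 at f = 0.10 and 1.225 at f = 0.50.
- Time-varying exposure, with enrolees moving to the class side: sqrt[(1/(3000(1+f)) + 1/(3000(1-f)))/(2/3000)] = 1.005 at f = 0.10 and 1.155 at f = 0.50.

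**The case against.** The best defence is that this is a delayed-start design, loosely worded. The first section 3 sentence would describe the control period and the second what comes after it; the match between 2 months of vouchers and a survey at 2-3 months supports this. The offer is optional, so few controls may use it. This stands for the surveys. It does not stand for the health metrics, because the documents never state the delayed start or say when control time ends.

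A reader might infer that the plan tells the analyst to keep enrolees as controls, and so will count up to three years of class-exposed time as control time. The documents do not support that. No section says labels are kept, and section 1's description of controls suggests that a person who enrols no longer qualifies. Misclassification is one possible outcome of a silent plan.

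The word *they* could mean the children. The stated purpose favours the controls, and children of 7 and older are community-track subjects in any case, so the gap remains on either reading.

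It is also fair to say that the crossover rule is missing because the SAP specifies no community-track analysis at all. Its panel, within-person framework could accommodate changing exposure. That explains the omission without supplying a rule.

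Finally, the protocol's front matter and section 11 were not available, so the absence of a rule is established only for the remaining text.

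**Conclusion.** The two section 3 sentences conflict with each other, and the second conflicts with sections 1 and 2. In the text available, the status of a community control after enrolment is undefined for the three-year health metrics. The plan should be corrected on this point; confidence is medium.

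The true size is unknown because uptake and timing are not given. The retained effect of about 91% (10% enrol) or 53% (50% enrol) is illustration only and rests on every assumption listed with it, including the window opening at study start and labels being kept. The main harm is an ambiguous and probably diluted estimate; loss of power is secondary at the planned size unless uptake is well above half. The point concerns the community track only, and the survey comparison is largely unaffected.

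**What to change.** 1. Reconcile the two section 3 sentences with each other and with sections 1 and 2 on whether, and when, community controls may take the classes.
2. Record enrolment dates. In the community health-metric analysis, do not count time after enrolment as control time, and state one rule in advance. Either end control follow-up at enrolment, or treat class exposure as time-varying. With the time-varying option, start class follow-up at the same point relative to class participation as for those who took the classes from the outset; time between enrolment and that point belongs to neither side. Ending follow-up at enrolment needs no such start date for later enrolees. Under either rule, adjust for predictors of enrolment, including the metrics from the 3-year look-back.
3. Take the control survey at 2-3 months before any class enrolment.
4. Flag recipients of vouchers or child education in the analysis data.

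The cost is a wording change in the protocol, a short community-track rule in the SAP, and recording of dates that the documents do not say are already held. On the simple model above, for 10-50% uptake, the standard error rises by about 3-22% if control follow-up ends at enrolment, or about 0.5-15% with time-varying exposure. Enrolment may be informative, so either rule depends on how well its predictors are measured.
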